# 1.5.2.5 Tacrolimus (Prograf®)

Tacrolimus (Prograf®, FK506) has been in wide clinical use for the prevention of allograft rejection since 1994 when the FDA approved it after several years of testing. Tacrolimus is a macrolide antibiotic which inhibits calcineurin after binding intracellularly to FKBP12 within T cells, inhibiting IL-2 transcription. Tacrolimus is invariably administered with other immunosuppressive agents but is known to be associated with several side effects including hypertension, diabetes, nephrotoxicity, hyperkalemia, dyslipidemia, pruritis, and neurologic sequelae (including tremor, ataxia, and extremely rarely central pontine myelinolysis), nausea, vomiting and diarrhea (see product monograph for details). In 205 kidney transplant recipients receiving tacrolimus, the principal AEs were neurologic (tremor [54%], headache [44%], insomnia [32%], parathesia [23%]) and gastrointestinal (diarrhea [44%], nausea [38%], constipation [35%]) complaints, hypertension (50%), and kidney dysfunction (52%); hyperkalemia (31%) and hyperglycemia (22% in previous non-diabetics) also occurred. The severity of these events appears to be dose dependent, with very high plasma levels also producing delirium, seizures, and coma. Complications can be minimized with the relatively low dose long-term therapy typically used in islet transplant trials.

# 1.5.2.6 Cyclosporine (Neoral®)

Cyclosporine is associated with renal dysfunction, tremors, hirsutism, hypertension, and gum hyperplasia.

# 1.5.2.7 Mycophenolate Mofetil (CellCept®) And Mycophenolate Sodium (Myfortic®)

CellCept® and Myfortic® are associated with diarrhea, leucopenia, vomiting, and evidence of higher frequency of certain types of infections. CellCept® and Myfortic® may increase the risk of developing lymphomas and other malignancies, particularly of the skin, and have been known to cause fetal harm when administered to a pregnant woman. Cases of progressive multifocal leukoencephalopathy, sometimes fatal, have been reported in patients treated with CellCept® or Myfortic®.

### 1.5.3 Risks of Study Procedures

The procedures involved with the care of research subjects undergoing clinical islet transplantation include risks pertaining to: a) blood draw testing, b) metabolic stimulation testing, c) the procedural risks of islet implantation (using either the percutaneous transhepatic or direct surgical cannulation of tributaries of the portal vein approach), and d) specific follow-up testing.

#### 1.5.3.1 Blood Draw Testing

Peripheral blood draws performed during these research studies will not exceed 450 mL per six-week period. The subject may experience some discomfort at the site of the needle entry, and there is risk of bruising at the site. There is a remote risk of fainting or local infection.

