## 7.6 Follow-up Visits

At  $75 \pm 5$  days following each islet transplant, insulin-independence will be assessed as the primary endpoint as defined above (please see Section 3.1.1) based on one week of frequent capillary blood glucose monitoring ending with a fasting clinic visit for determination of HbA1c, fasting serum glucose and c-peptide, and serum glucose and c-peptide 90-minutes after ingestion of Boost®. This information also allows for the calculation of the  $\beta$ -score, a composite index of

islet graft function. Other self-glucose monitoring information captured at this visit will enable calculation of the Clarke and HYPO scores of hypoglycemia awareness and severity, respectively, the hypoglycemia fear survey, and the MAGE and LI scores of glycemic lability. This assessment will be repeated at 6, 9, 12, 15, 18, 21, and 24 months post-transplant.

The acute c-peptide and insulin responses to IV glucose and arginine will be performed during a two night admission to the GCRC scheduled at 3 months following each transplant, and at 12 and 24 months after the last transplant. The IV glucose test will be administered as a frequently-sampled intravenous glucose tolerance test in order to calculate insulin sensitivity ( $S_I$ ) and the disposition index (DI). The IV arginine test will be performed with glucose-potentiation in insulin-independent recipients and those taking  $\leq 0.1$  U/kg of daily insulin to optimize glycemic control in order to determine the  $\beta$ -cell secretory capacity at day 75 and at 12 months. Also at 3, 12, and 24 months, 72-hours of continuous glucose monitoring will be performed.

At 6 and 14 months post-transplant, paired hypoglycemic and euglycemic clamps will be performed one week apart, in randomized order, each after a one night admission to the GCRC.

At 12 months following the first transplant retinal photography will be performed.

Clinic visits for immunosuppression drug monitoring will occur monthly for the first two years and quarterly thereafter. Additional tests will be repeated as indicated in the timeline provided in the appendix.

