#### 7.7 Visit Windows

The visit for determining the primary endpoint of insulin-independence will occur at  $75 \pm 5$  days following each islet transplant. All other visits are scheduled on a monthly basis from the last transplant (for the first 9 months; quarterly thereafter  $\pm$  14 d until 24 months, then biannually  $\pm$  30 d), and should occur within 7 days (plus or minus) of the calendar date for the transplant. For example, a subject receiving a transplant on the  $14^{th}$  of one month should have follow-up visits between the  $7^{th}$  and  $21^{th}$  of subsequent months. A second transplant resets this schedule, except for the retinal photography.

Study visits should take place within the time limits specified on the Schedule of Events (Appendix 1).

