### Approach:

The standard IV arginine stimulation test (AST) involves blood sampling at baseline (t = -5 & -1 min) and at t = 2, 3, 4, & 5 min post-injection of a maximally stimulating dose of arginine hydrochloride (5 g or 50 mL of 10% solution, Pharmacia & Upjohn, Kalamazoo, MI) over 1 min starting at t = 0. After collection, the protease inhibitors trasylol and leupeptin are immediately added to the blood samples, which are placed on ice, centrifuged at 4 °C, and frozen at -80 °C until biochemical analysis. The acute C-peptide and insulin responses to arginine (ACRarg & AIRarg), defined as the mean of the post-injection C-peptide or insulin values minus the mean of their baseline values, provide measures of  $\beta$ -cell function. The total amount of blood sampled is 24 mL.

The AST may be extended to a glucose-potentiated arginine (GPA) test. This will only be done in insulin-independent subjects or those taking  $\leq 0.1$  U/kg of insulin daily to optimize their glycemic control. After the baseline AST described above, a hyperglycemic clamp technique utilizing a variable rate of 20% and 10% glucose solutions is performed to achieve a glucose

level of 230 mg/dL. Blood samples are taken every 5 min, centrifuged, and measured at bedside with a portable glucose analyzer (YSI 1500 Sidekick; Yellow Springs Instruments, Yellow Springs, OH) in order to adjust the infusion rates and achieve the desired glucose concentration. After 45-minutes of the glucose infusion, the 5 g arginine pulse is injected again with identical blood sampling. It has been demonstrated that the first administration of arginine has no effect on the subsequent response to arginine using this protocol. Then, a 2-hour period without glucose infusion takes place to avoid the priming effects of hyperglycemia on insulin release. At the end of the 2-hour period, a hyperglycemic clamp is performed to achieve a glucose level of 340 mg/dL. Forty-five minutes after initiation of the glucose infusion, another arginine pulse is injected with identical blood sampling. The total amount of blood sampled is 92 mL.

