Blood samples will be taken every 5 min, centrifuged, and measured at bedside with a portable glucose analyzer (YSI 1500 Sidekick; Yellow Springs Instruments, Yellow Springs, OH) to adjust the glucose infusion rate and achieve the desired glucose concentration. Additional blood samples will be taken at t = 20, 40, 60, 80, 100, 120, 140, 160, 180, 200, 220, and 240 min for biochemical analysis and verification of the glucose levels. The total amount of blood sampled will not exceed 168 mL. A questionnaire will be administered every 20 min during the study in order to quantitate autonomic symptoms as the sum of scores ranging from 0 (none) to 5 (severe) for each of the following symptoms: anxiety, palpitations, sweating, tremor, hunger, and tingling  $^{167}$ .

Hyperinsulinemic euglycemic clamp: Because hyperinsulinemia inhibits endogenous insulin secretion, glucagon secretion, and endogenous glucose production, a euglycemic clamp will be performed to assess the impact of insulin per se on endogenous glucose production independent from hypoglycemia. Subjects will undergo the euglycemic clamp in randomized order with the hypoglycemic clamp at least 1 week but not longer than 1 month apart. The hyperinsulinemic euglycemic clamp will be conducted as described for the hypoglycemic clamp above, but with the target glucose 90 mg/dL for the entire 240 min study.

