<sup>26 General flow cytometry on T and B lymphocyte subsets will be performed using a four-color panel. In order to obtain absolute cell counts and for quality control purposes, a CBC with differential will be performed in parallel with every flow cytometry experiment. General flow will be performed every 6 months while subjects are on the waitlist. In addition to the time points listed in the table above, late time points (months 15, 18, and 21 after the first islets transplant) will be added if the subject is still in study follow-up.

<sup>27 The HiD B cell tube refers to using a large number of different fluorochrome conjugated markers in the same tube (11 colors). High definition flow will be performed every 6 months while subjects are on the waitlist. In addition to the time points listed in the table above, high definition flow will be performed at late time points (months 15, 18, and 21 after the first islets transplant) if the subject is still in study for follow-up.

<sup>28 CD19 separation will be performed twice while subject is on the waiting list prior to transplantation and at least once during a late time point (after 12 months).  DNA will be extracted from peripheral blood leukocytes every three months while subjects are on the waitlist to be transplanted and will be banked at the indicated time points following transplant.

<sup>30 The T cell ELISpot screen will be performed at baseline and repeated every six months while the subject is on the wait list (scheduling can be done at the discretion of other studies and the subject; also, testing will not be performed if the subject has a viral infection.) The screen will be performed using dominant T cell epitopes and pools of peptides for islet antigens. The read-outs will be IFN-γ and TGF-β secretion.

<sup>31If the T cell ELISpot is positive, the specificity of reacting T cells (checked against a panel of peptides) will be profiled and the secretion of different cytokines will be monitored. The sample volume for the T cell ELISpot screen and specificity is 18 ml per time point.

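### For subjects having the full arginine test, two clamps at their stated maximum plus that test leave 22 mL of the 450 mL six-week blood limit at Day 365, so the limit would very probably be exceeded; the clamp timing is also stated three ways.

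*Protocol*

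**What the plan says.** Section 1.5.3.1 sets the limit without exception: "Peripheral blood draws performed during these research studies will not exceed 450 mL per six-week period".

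The volumes are given elsewhere in the Protocol:

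- **Clamps (9.1.2.12).** For the hypoglycemic clamp, "The total amount of blood sampled will not exceed 168 mL". The second clamp has the same procedure: "The hyperinsulinemic euglycemic clamp will be conducted as described for the hypoglycemic clamp above". The two are to be "at least 1 week but not longer than 1 month apart".
- **GPA (9.1.2.11).** For the full test, "The total amount of blood sampled is 92 mL". It is given to insulin-independent subjects and to those on no more than 0.1 U/kg of insulin daily. The others have the arginine stimulation test (AST) alone, at 24 mL.
- **FSIGT (9.1.2.8).** Twenty-four timed samples, each assayed for insulin, C-peptide and glucose. No volume is stated.
- **Other stated volumes.** For the T cell ELISpot, "The sample volume for the T cell ELISpot screen and specificity is 18 ml per time point" (Appendix 1, footnote 31). The alloantibody sample is 2 mL (9.2.1.2).

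Appendix 1 marks counter-regulation (the paired clamps), GPA and FSIGT all at Day 365, with a ±14-day window. Section 7.7 tells sites to keep to the Appendix 1 windows.

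Two other sections time the clamps differently. Section 3.1.3 allows 365 ±60 days after the last transplant, with the GPA at 365 ±14. Section 7.6 says: "At 6 and 14 months post-transplant, paired hypoglycemic and euglycemic clamps will be performed one week apart".

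**The concern.** The 450 mL limit is the Protocol's stated protection against excessive research blood sampling. A ±14-day window spans 28 days, so everything scheduled inside it falls within one six-week period. Three procedures then use almost the whole allowance before the FSIGT is counted. Also marked at Day 365, with no volume given, are CBC, chemistry, lipids, HbA1c, the mixed-meal test, CMV/EBV PCR, drug levels, autoantibody, flow cytometry, clone tracking, CD19+ separation and archived serum, cells and RNA.

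If the limit cannot be kept, subjects are told of a protection that the schedule does not deliver. The largest draw falls on those with the best graft function, because they have the full GPA.

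The conflicting timings matter in their own right. Whether a site keeps the limit depends on which section it follows, and the late counter-regulation measurement would not be taken at a common time.

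**Working it through.** The 450 mL figure is given without a derivation, so there is nothing to reproduce. The check adds the stated volumes.

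**Samples and rates**

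- FSIGT: 3 baseline + 21 post-injection = 24 samples.
- AST: 2 baseline + 4 post-injection = 6 samples in 24 mL, so 24 / 6 = 4 mL per sample.
- GPA: three arginine pulses at 24 mL = 72 mL, leaving 92 − 72 = 20 mL for bedside glucose samples. Assuming 18 of these (every 5 minutes in two 45-minute clamps), that is about 1.1 mL each.

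**Subjects having the full GPA, clamps at their ceiling**

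- Clamps + GPA: 2 × 168 + 92 = 428 mL; remaining 450 − 428 = 22 mL.
- Break-even FSIGT volume with every other tube at zero: 22 / 24 = 0.92 mL per sample.
- Adding T cell ELISpot and alloantibody: 428 + 18 + 2 = 448 mL; remaining 2 mL, or 2 / 24 = 0.08 mL per FSIGT sample.

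The total for clamps + arginine test + FSIGT, with v the assumed FSIGT volume per sample, is 428 + 24v for full-GPA subjects. For AST-only subjects it is 2 × 168 + 24 + 24v = 360 + 24v.

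| v (mL, assumed) | Full GPA (mL) | AST only (mL) |
|---|---|---|
| 0.5 | 440 | 372 |
| 1 | 452 | 384 |
| 2 | 476 | 408 |
| 4 (the AST's rate) | 524 | 456 |

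**AST-only subjects.** Break-even is (450 − 360) / 24 = 3.75 mL per sample. With the 20 mL of ELISpot and alloantibody it falls to (450 − 380) / 24 = 2.9 mL.

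**How far below the ceiling the clamps would have to be.** For a full-GPA subject with a 4 mL FSIGT and the same 20 mL: (450 − 92 − 96 − 20) / 2 = 121 mL per clamp, which is 47 / 168 = 28% under the ceiling.

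**Separating the clamps from the other tests.** The clamps alone take at most 336 mL. GPA, FSIGT at 4 mL, T cell ELISpot, alloantibody and the 10 mL B cell ELISpot take 92 + 96 + 18 + 2 + 10 = 218 mL. Each block is under 450 mL before the tubes of unstated volume.

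**Whether month 14 secures that separation.** Month 14 is about day 426 (14 × 30.44). The GPA and FSIGT may fall as late as day 365 + 14 = 379. No window is given for the month-14 clamps. With section 7.7's ±7 days the first clamp could fall on day 419, a gap of 40 days. With its ±14 days for later visits, day 412 gives 33 days. Both are short of 42.

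**The case against.** A reader might infer that the Protocol's own figures break the limit. They do not. The stated volumes that Appendix 1 clearly places at Day 365 reach 448 mL, and every total above 450 mL needs an FSIGT volume that the Protocol leaves to a core-laboratory procedure. A figure of 458 mL without the FSIGT can be reached by adding 10 mL for the B cell ELISpot, because footnote 32 of Appendix 1 lists month 12. The Appendix 1 grid does not mark that assay at Day 365, so the conclusion should not rest on it.

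Three further points stand. The 168 mL is a ceiling, so 336 mL is a maximum. AST-only subjects may stay within the limit. Sections 3.1.3 and 7.6 leave room for a compliant schedule, so a breach is not forced across the document.

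It would also go too far to say that subjects are harmed or that the anemia safety endpoint is distorted. Section 1.5.2.4 does cite more anemia with sirolimus (33% vs 21%). But section 1.5.3.1 lists only discomfort, bruising, fainting and local infection as draw risks, and Day 365 is the last scheduled visit after the final transplant. The Day 75 primary endpoint is not affected.

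What the objection does not remove is the margin. To comply under Appendix 1 with clamps at their ceiling, 24 samples assayed for three analytes, together with every tube of unstated volume, would have to fit in 2 mL.

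**Conclusion.** The point holds as a conflict between the stated limit and the Appendix 1 schedule, and should be fixed. For subjects having the full GPA (insulin-independent or on no more than 0.1 U/kg daily), 428 to 448 of the 450 mL is used before the FSIGT and the tubes of unstated volume, so the limit would very probably be exceeded. This rests on three assumptions: clamps at their stated maximum, the euglycemic clamp drawing as much as the hypoglycemic one, and all tests falling inside the Day 365 ±14 window. The size of the excess depends on the unstated FSIGT volume: 2 mL at 1 mL per sample, 26 mL at 2 mL and 74 mL at 4 mL, for clamps, GPA and FSIGT only. For AST-only subjects the result is open.

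Separately, and without any assumption, the late clamp timing is stated in three incompatible ways. A reader might take month 14 as the ready answer. The documents do not settle which timing is right, and month 14 without a window does not guarantee six weeks between the blocks.

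**What to change.** - Reconcile the clamp timing and its window across Appendix 1, section 3.1.3 and section 7.6, and reconcile the result with section 1.5.3.1.
- State the FSIGT volume and the total Day 365 volume, separately for full-GPA and AST-only subjects.
- Confirm that the cumulative draw in any six-week period under the reconciled schedule stays within 450 mL, or correct the stated limit.
- Settle whether the B cell ELISpot is drawn at month 12, since footnote 32 and the Appendix 1 grid differ.

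The cost is schedule wording and a table of volumes; no test is added. If the reconciled timing falls after month 12, the text must say that follow-up for this one assessment runs past the 12 months after final transplant given as the study duration in the Synopsis.

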#### 1.5.3.2 Metabolic Stimulation Testing

The risks associated with metabolic testing are generally regarded as minor. Placement of IV cannulae may be associated with pain and discomfort at the puncture site, bruising, bleeding, displacement, interstitial infusion of fluids; rarely local vein thrombosis, infection or thrombophlebitis may develop.

The administration of bolus glucose or insulin by mouth or intravenously may lead to acute hypoglycemia or hyperglycemia; or rarely ketoacidosis may occur. The administration of bolus arginine intravenously may cause a transient metallic taste in the mouth; allergy is rare. The administration of insulin during the FSIGT, euglycemic clamp, or hypoglycemic clamp studies could lead to a greater degree of hypoglycemia than expected, but would be rapidly corrected with intravenous glucose. The stable isotope of glucose infused during the glycemic clamps carries no additional risks

#### 1.5.3.3 The Procedural Risks of Islet Transplantation

Islets may be infused into the hepatic portal vein either by an open surgical approach or by a percutaneous transhepatic approach.

#### **Open Surgical Approach**

This procedure is usually carried out under general anesthesia, but can be performed occasionally under local anesthesia if required. The potential risk of acute bleeding is anticipated to be less with a controlled operative approach as opposed to a percutaneous approach, especially where a transplant site does not have access to local expertise in advanced interventional radiological procedures. Access to a tributary of the portal vein using the open technique requires a surgical incision for exposure, and direct cannulation of a branch of the middle colic vein, the inferior mesenteric vein, a tributary of the superior mesenteric vein or direct cannulation of a small omental vein. Potential acute surgical risks include bleeding at the surgical site, portal thrombosis, hepatic abscess, hepatic infarction, mesenteric ischemia and mesenteric thrombosis. The general risks of surgery include wound infection, wound hernia, adhesional bowel obstruction, deep vein thrombosis and pulmonary embolism. Risks associated with anesthesia include difficulties with airway management, cardiac arrhythmias and drugrelated anaphylactic reactions. Pain and discomfort at the surgical site is expected in the early period following surgery, and may be reduced by administration of opiate, opioid or nonsteroidal analgesic medications. If an ileus develops, a prolonged hospital stay may be anticipated.

#### **Percutaneous Transhepatic Approach**

Transhepatic portal vein catheterization may have complications and morbidity similar to those associated with transhepatic cholangiography and percutaneous core needle biopsies of the liver. The most common morbidity of transhepatic portal vein catheterization (percutaneous approach) is abdominal or right shoulder tip referred pain. In addition, liver hemorrhage and intraabdominal bleeding have been known to occur as well as pneumothorax, hemothorax, damage to the gall bladder, or pleural effusion. If a percutaneous approach is used, ablative techniques are employed to reduce the risk of acute bleeding after catheter withdrawal. This procedure is usually carried out in interventional radiology using a combination of ultrasound and fluoroscopic guidance with administration of radio-opaque contrast media to assure proper localization of the infusion. Though the use of contrast media will be minimized, some subjects can develop local or systemic reactions to such products.

#### Risk of Bleeding after Percutaneous Islet Transplantation

In the 158 islet transplant procedures submitted to the Collaborative Islet Transplant Registry (CITR), the reported SAEs associated with bleeding include hemoperitoneum (n=1), intraabdominal bleed (n=2), low hemoglobin (n=1), right hemothorax (n=1), and subcapsular hematoma of the liver. Subcapsular hematoma of the liver following percutaneous transhepatic injection of islets into the portal vein in two cases has also been reported to the International Islet Transplant Registry. No surgical intervention was necessary. One instance of injury to hepatic artery leading to death during percutaneous transhepatic catheterization of

the portal vein has been reported previously to the Islet Transplant Registry. Reports on intraabdominal (n=1) and intrathoracic bleeding (n=1) have been published. The risk of significant hemorrhage after percutaneous islet transplantation defined as a drop in hemoglobin of more than 25 g/L or the need for transfusion or surgery was 9% in the Edmonton series. Subsequently, a further increase in risk of bleeding has been observed by the Edmonton program and has been attributed in part to concomitant aspirin therapy. The risk has since been ameliorated by avoidance of pre-transplant aspirin and more effective measures to seal the catheter tract in the liver. When effective methods are used to ablate the transhepatic portal catheter tract, bleeding can be avoided completely; at the University of Miami D-Stat thrombostatic agent has been used to seal the catheter tract and has avoided risk of bleeding. At the University of Minnesota, no bleed-related complications occurred in 20 consecutive subjects when the catheter tract was sealed with combined coils and gelfoam^22.

